Given these shortcomings in this evolving area of clinical research, a comprehensive characterization of myocardial injury in patients with COVID-19 infection and the identification of clinical predictors for its occurrence could allow the development of predictive models, thus helping clinicians in the disease phenotyping and the early assessment of the risk of unfavourable outcome and improving a fast determination of most appropriate treatments and clinical paths, efficient planning and use of clinical resources in terms of treatment type and units (such as intensive care or coronary intensive care). In addition, the identification of clinical predictors and/or protective factors for myocardial injury in COVID-19 infection may pave the way for the development of specific therapeutic strategies aiming to reduce the impact of myocardial injury on COVID-19-related morbidity and mortality. Finally, assessing the long-term cardiovascular impact of myocardial injury in COVID-19 infection could help clinicians in the prognostic stratification and the choice of therapeutic strategies in the post-acute COVID-19 phases, possibly identifying those patients that may need a more aggressive therapy and a closer follow-up.

A comprehensive characterization of myocardial injury in COVID-19 infection is still lacking, and no clinical predictors of myocardial injury has been identified yet. Moreover, the long-term cardiovascular outcome of myocardial injury in the post-acute COVID-19 phase is largely unknown. We thus hypothesize that:

- that clinical predictors and/or protective factors (including vaccination status) for myocardial injury in COVID-19 infection could be identified, thus allowing the development of predictive models that could help clinicians in the disease phenotyping,

the early assessment of the risk of unfavourable outcome and improving a fast determination of most appropriate management;

- that myocardial injury in COVID-19 patients could be associated with a worse clinical course characterized by higher incidence of in-hospital complications and need for escalation of therapies;
- that myocardial injury in COVID-19 patients could be associated with a worse angina status and quality of life as well as with a higher rate of adverse cardiovascular events in the post-acute COVID-19 phase, thus helping in the prognostic stratification of COVID-19 patients and identifying those that may need a more aggressive therapy and a closer follow-up.

OBJECTIVES

Primary objective

To identify clinical predictors of myocardial injury in patients hospitalized for COVID-19 infection since the introduction of vaccines (i.e., March 1, 2021).

Secondary objectives

1. To evaluate if the presence of myocardial injury during the index hospitalization for COVID-19 is associated with a worse in-hospital clinical course in terms of in-hospital complications and need for aggressive therapies.
2. To evaluate if the presence of myocardial injury during the index hospitalization for COVID-19 are associated with a worse angina status and quality of life (evaluated using the Seattle Angina Questionnaire [SAQ] summary score (15)) at 12-months follow-up.
3. To evaluate if the presence of myocardial injury during the index hospitalization for COVID-19 predicts a worse clinical outcome in terms of major adverse cardiovascular events (MACE) (defined as the composite of cardiovascular death, ischemic heart disease [acute or chronic coronary syndromes], stroke/transient ischemic attack [TIA] and hospitalization for heart failure), dysrhythmias (defined as the composite of new-onset atrial fibrillation and/or ventricular arrhythmias), inflammatory heart disease (pericarditis and/or myocarditis) or thrombotic disorders (pulmonary embolism, deep vein or superficial vein thrombosis) at 12-months follow-up.

METHODS

Study design

Retrospective and prospective observational study.

Population

All consecutive patients hospitalized at Policlinico Universitario A. Gemelli IRCSS since March 1, 2021, with a diagnosis of SARS-CoV-2 infection (≥ 1 positive nasopharyngeal swab) and at least one value of high-sensitivity cardiac troponin I (hs-cTnI) measured during the index hospitalization will be enrolled. Given that the patients are unable to physically sign the informed consent form due to epidemiological reasons (contamination of papers by SARS-CoV-2), each patient will verbally declare the consent to “Consenso al trattamento dei dati personali e dei campioni biologici a scopo di ricerca – no profit”, “modulo di dichiarazione della volontà espresso ai fini del consenso informato generale alle cure” and “modulo dossier sanitario – richiesta di oscuramento/deoscuramento di eventi/episodi” at the presence of at least two witnesses.

Inclusion criteria

- Age ≥ 18 years;
- Overt COVID-19 infection (molecular nasopharyngeal swab positive for SARS-CoV-2 ≥ 1);
- Patient with at least a high sensitivity Troponin I measured during hospitalization course.
- Available data on vaccination.
- Verbal informed consent

Exclusion criteria

- Age <18 years;
- Patient in whom at least one high sensitivity Troponin I value measured during the course of hospitalization is not available.
- No data available on vaccination status.

Variables and procedures

This study will make use of Data Mart COVID-19 developed within Generator Real World Data Unit. The Data Mart COVID-19 belongs to the family of the diagnostic and prognostic mini-bots developed within the Generator Real World Data Unit project in which artificial intelligence solutions (such as text mining) are adopted to automatically extract both structured and unstructured data from hospital databases of patients infected from SARS-CoV-2. Feature selection and machine learning algorithms can be applied to develop diagnostic and prognostic support systems for clinicians.

The specific data that which will be exploited are:

- Demographics data;
- Patient comorbidities, vital signs and symptoms at the time of admission;
- Laboratory analysis;
- In-hospital complications (e.g.: need for non-invasive or invasive ventilation, access to intensive care unit, length of hospitalization, use of glucocorticoids or antibiotics, death);

- Blood gas exchange information;
- Radiological reports;
- Medications at the time of admission, during hospitalization and at the time of discharge;
- Vaccination status.

Clinical follow-up

All patients will undergo a clinical follow-up by telephonic interview and/or clinical visit at 12 months from hospital discharge, during which the incidence of MACE, dysrhythmias, inflammatory heart disease and/or thrombotic disorders (both as incidence of the composite and as incidence of each individual components) in the past months will be investigated, the SAQ will be administered and the SAQ summary score will be collected.

ENDPOINTS

Primary endpoint

To assess for the presence of clinical predictors for the occurrence of myocardial injury, defined as at least one value of hs-cTnI >99th percentile upper reference limit (16), in patients hospitalized for COVID-19 infection.

Secondary endpoints

1. The occurrence of myocardial injury during the index hospitalization for COVID-19 infection will be correlated with in-hospital complications (defined as the composite of the need for non-invasive or invasive ventilation, access to intensive care unit, length of hospitalization, use of glucocorticoids or antibiotics, and death).
2. The occurrence of myocardial injury in patients during the index hospitalization for COVID-19 infection will be included in a prediction model and correlated with future cardiovascular events (MACE), dysrhythmias, inflammatory heart disease and/or thrombotic disorders at 12-months follow-up.
3. The occurrence of myocardial injury during the index hospitalization for COVID-19 infection will be correlated with angina status and quality of life, evaluated using the SAQ summary score, at 12-months follow-up.

STATISTICAL ANALYSIS PLAN

Sample size calculation

A comprehensive characterization of myocardial injury in COVID-19 infection is still lacking, and no clinical predictors of myocardial injury has been identified yet. Moreover, the long-term cardiovascular outcome of myocardial injury in the post-acute COVID-19 phase is largely unknown. Thus, this configures as a pilot study on large-scale cohort. As such no formal sample size calculation is needed. However, based on the COVID-19 datamart of our clinical institution and on inclusion criteria, we expect to include in the study around 2000 patients hospitalized with COVID-19. Such a sample size is largely consistent with common rules of thumb for pilot studies. In addition, the estimated sample size is largely consistent with the van Smeden metamodels related to the new statistical approaches for the development of clinical prediction models (17). The square root of the mean squared prediction error (rMPSE) and mean absolute prediction error (MAPE) may be approximated via the results of these. Lower values for rMSPE and MAPE indicate better performance. For instance, at a sample size of $N=400$, with $P=8$ candidate predictors and an expected event fraction of $\frac{1}{4}$, the predicted out-of-sample rMPSE would be 0.065 when ML model (without variable selection) is applied, and 0.053 for Ridge regression; MAPE would instead be 0.045 for the ML model and 0.038 for the Ridge regression.

Statistical analysis

All demographic, clinical and laboratory characteristics will be summarized by descriptive statistics techniques. In depth, qualitative variables will be expressed by absolute and relative percentage frequencies. Quantitative variables, indeed, will be reported either as mean and standard deviation (SD) or median and interquartile range (IQR), respectively in the case they were normally or not normally distributed. Their distribution will be previously assessed by the Shapiro Wilk test. Between groups differences in the demographic, clinical, laboratory and pathologic features will be assessed by the Chi Square or the Fisher's exact test as for qualitative variables, with Yates correction, as appropriate, whilst quantitative variables will be evaluated either by the Student's t test or the Mann-Whitney U test, according to their distribution. Univariable and multivariable logistic regression models will be performed to evaluate the presence of clinical predictors for the occurrence of myocardial injury in COVID-19 infection. Results will be expressed as odds ratio (OR) with 95% confidence interval (CI). Model calibration performances will be evaluated via the Hosmer-Lemeshow goodness of fit test with 10 groups. Model performance will be assessed through receiver-operator characteristic (ROC) curve analysis by reporting the area under the curve, sensitivity, specificity and +/- likelihood ratio (LR). Univariable and multivariable logistic regression analysis will be performed also to assess the association of myocardial injury in COVID-19 infection with in-hospital complications and need for aggressive therapies.

Univariable and multivariable multiple linear regression will be instead used to assess

whether SAQ summary score at 12-months follow-up is affected by myocardial injury in patients with COVID-19 infection.

Finally, to assess whether the presence of myocardial injury during COVID-19 predicts a worse outcome, in term of both MACEs at 12 months and single components, uni- and multivariable interaction proportional hazard Cox regression models will be computed. We will consider, as for MACEs, time to first event, and for each component, time to each event. To evaluate combined effects between each clinical/laboratory predictor and presence/absence of Myocardial Injury (MI), multivariable interaction Cox models will be fitted, and the interaction hazard ratios (IHR) evaluated. In particular, for each predictor, one interaction Cox model will be fitted. In this framework, IHR = 1 indicates no synergy between predictor and MI, IHR <1 expresses a reduction of hazard due to the synergy, while IHR >1 an increased hazard. The interaction parameters (IHR) will be interpreted as difference (in HR terms) of the predictor and MI (absence of MI as reference category). Proportionality of the hazard functions will be assessed by visual inspection of hazard plots and Schoenfeld residuals. When proportionality was doubtful, weighted Cox regression models would be fitted.

A two-tailed analysis will be performed and a p value <0.05 will be considered as statistically significant. Statistical analyses will be performed using R software version 4.2.1 (CRAN®, R Core 2021) (and its packages *survival*, *survminer*, *coxphw* and *Hmisc*) (18).

Data privacy and data protection

Privacy issues related to this project have been analyzed with Policlinico Gemelli Data Protection Officer (D.P.O.). As a GENERATOR RWD study, this project will be compliant with GDPR Italian and European directives and regulation (EU Directive 2016/679 and under Italian Laws: Decreto Legislativo 196/2003, Decreto Legislativo 101 2018, Autorizzazione Generale Garante 9/2016)

The guidelines for data privacy are covered by two main documents prepared with the D.P.O.:

- Generator main document “Linee Guida Utilizzo Real World Data” which prescribes the governance mechanisms for Generator through two main bodies (Comitato di Supervisione and Comitato Operativo) where representatives appointed from IRCSS and other key Units of Policlinico participate and have mandate to decide;
- “Orizzonte Normativo Real World Data” prepared by the D.P.O., which provides the directives for the execution of any Generator study to assure its compliance with European and Italian GDPR directives.

All RWD studies have research purposes and therefore consent-related procedures are consistent with European Directive 2016/679. The data architecture which supports RWD studies has been defined to provide the highest degree of protection, in accordance with all GDPR and security requirements. In this respect, RWD provides “protection by design” in each step of the process.

Significance and innovation

This study will provide a detailed characterization of myocardial injury in patients with COVID-19 and its role in determining the different clinical courses of SARS-CoV-2 infection. Moreover, the aim of study is to identify, for the first time, the clinical predictors of the occurrence of myocardial injury in patients with COVID-19 infection that could allow the development of predictive models as well as help clinicians in the early assessment of the risk of myocardial injury and the prevention of the associated unfavourable outcomes. Furthermore, this study will characterize the cardiovascular outcomes in the post-acute COVID-19 phase, and it will evaluate for the first time the long-term clinical outcomes of patients who experienced myocardial injury, possibly paving the way for the implementation of specific therapies aiming to reduce the cardiovascular risk and the long-term sequelae of COVID-19.

References

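### Eligibility admits patients hospitalized *with* a positive swab while the objectives concern patients hospitalized *for* COVID-19, so a troponin drawn before an in-hospital infection can be scored as COVID-19 myocardial injury

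*Protocol*

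**What the plan says.** Under Methods, Population, the protocol enrols consecutive inpatients since March 1, 2021 "with a diagnosis of SARS-CoV-2 infection (≥ 1 positive nasopharyngeal swab") who have "at least one value of high-sensitivity cardiac troponin I (hs-cTnI) measured during the index hospitalization". The inclusion criteria repeat both conditions: "Overt COVID-19 infection (molecular nasopharyngeal swab positive for SARS-CoV-2 ≥ 1") and "Patient with at least a high sensitivity Troponin I measured during hospitalization course". Neither the swab nor the troponin sample is dated relative to the other, and the swab is not dated relative to admission. The exclusion criteria cover age, absence of a troponin value and absence of vaccination data. Infection acquired during the stay is not mentioned.

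The primary endpoint is injury "defined as at least one value of hs-cTnI >99th percentile upper reference limit (16), in patients hospitalized for COVID-19 infection". The primary objective likewise seeks "clinical predictors of myocardial injury in patients hospitalized for COVID-19 infection". The secondary objectives and endpoints use the same flag as the exposure, for example: "The occurrence of myocardial injury during the index hospitalization for COVID-19 infection will be correlated with in-hospital complications".

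The section on sample size expects around 2000 patients, says that this count rests on the data mart and the inclusion criteria, and describes them as hospitalized *with* COVID-19.

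**The concern.** The entry rules and the question are worded for different populations. The entry rules ask for a positive swab and a troponin in the same stay, in any order and any distance apart. The question concerns people whom COVID-19 brought into hospital.

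The gap matters for one kind of patient. Suppose someone is admitted with a negative swab, has a raised hs-cTnI on day 1 and is first swab-positive on day 12. Every inclusion criterion is met, no exclusion applies, and the day-1 value satisfies the threshold. The patient would be scored as having myocardial injury in COVID-19, although the raised value came before the infection.

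Counting such values can only add events; it cannot remove any. The added events would reflect other causes of cardiac injury, and the risk factors for those causes could then appear as predictors in the primary model. The same flag is the exposure for in-hospital complications, for the 12-month cardiovascular outcomes and for the angina score. The in-hospital composite also includes length of stay, and a patient first positive late in the stay has a long stay by construction, part of it before infection.

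**Working it through.** **Text check**

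| Element | Where in the protocol | Timing or population stated |
|---|---|---|
| Enrolment | Population | admitted *with* a diagnosis; swab undated |
| Infection | Inclusion criteria | one positive molecular swab; undated |
| Troponin | Population; Inclusion criteria | any time in the stay |
| Hospital-acquired infection | Exclusion criteria | not addressed |
| Injury | Primary endpoint | any one raised value; admitted *for* COVID-19 |
| Target population | Primary and secondary objectives; secondary endpoints | admitted *for* COVID-19, or index stay *for* COVID-19 |
| Expected number | Sample size calculation | based on the inclusion criteria; hospitalized *with* COVID-19 |

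If infection caused the admission, no troponin of that stay can precede it. A pre-infection value can therefore count only if patients infected after admission are enrolled. The criteria allow this, and the objective and endpoint wording does not.

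**Illustrative size**

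The protocol has no figure of its own on this point to reproduce. Inputs:

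- N = 2000 (Sample size calculation).
- Event fraction = 1/4. The protocol gives this only in a worked illustration for 400 patients and 8 candidate predictors. Using it for this cohort is an assumption.
- h = share infected after admission. Not in the document; assumed 1% to 10%, with 0 as the limiting case.
- q = share of those with a raised hs-cTnI before infection. Not in the document; assumed 10% to 40%.

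Events = 2000 × 1/4 = 500. Affected patients = N × h × q. Share of events = affected / 500.

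| h | q | Affected patients | Share of 500 events |
|---|---|---|---|
| 0 | any | 0 | 0 |
| 1% | 10% | 2 | 0.4% |
| 1% | 40% | 8 | 1.6% |
| 5% | 25% | 25 | 5% |
| 10% | 10% | 20 | 4% |
| 10% | 40% | 80 | 16% |

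These are upper bounds on misclassification. A patient who is raised before infection and again afterwards remains an event under any sensible definition; only those raised solely beforehand change status. If post-infection injury occurred in 1/4 of these patients independently of the earlier value, the affected numbers would be multiplied by 3/4: 2 becomes 1.5 (0.3% of 500) and 80 becomes 60 (12%).

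**The case against.** The strongest reply is that the protocol already limits the question. The primary objective, the primary endpoint and all the secondary objectives and endpoints speak of hospitalization *for* COVID-19. The requirement of overt infection and the recording of symptoms at admission fit that reading, though neither settles it. On that reading the day-12 patient is out of scope, the number of misclassified events is zero, and aligning eligibility with the objective would be enough without a time window.

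Part of this stands. It rules out saying that pre-infection values *will* be counted: they can be, if such patients enter. It does not remove the point. No inclusion or exclusion criterion implements *for*, the expected 2000 is tied to the inclusion criteria and described as hospitalized *with* COVID-19, and the data mart is described as covering infected patients, not patients admitted because of infection. An automated extraction would follow the criteria as written.

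Two further objections also stand. The size rests entirely on assumed shares. And the first positive swab is not the date of infection, so a window anchored to it has errors of its own.

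**Conclusion.** The point holds as an unreconciled conflict between the eligibility criteria and the objectives, with a specific consequence: if patients infected after admission are enrolled, a troponin from before infection can define the primary outcome and the exposure in the secondary objectives. Eligibility and the outcome definition are both stated in this protocol, so this is not a detail left for a later analysis plan.

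The size cannot be derived from the document. It is 0 if everyone was admitted for COVID-19. With 1–10% infected in hospital, 10–40% of those with an earlier raised value, and the illustrative event fraction of 1/4, it is at most roughly 0.4–16% of events.

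A reader might infer that a known and sizeable share of injury cases precedes infection, or that predictors of unrelated cardiac injury are bound to enter the model. The document supports neither, because it gives no share of hospital-acquired cases and no share with an earlier raised value. What is established is that the rules permit the error.

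**What to change.** 1. Reconcile the two wordings in the eligibility criteria. Either restrict entry to infection present at admission, or state that hospital-acquired cases are included and word the objectives to match. The first option removes the example patient by itself; the time window matters most if hospital-acquired cases are kept.
2. Define the qualifying troponin relative to the first positive swab: count only hs-cTnI values from a prespecified short interval before that swab (e.g. 48 h, to allow for swab delay) to discharge, and require at least one value in that window for eligibility.
3. Leave patients with a raised value only before the window out of the injury-free group, at least in a sensitivity analysis, and vary the width of the window.

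The costs are modest but real. Patients with no value in the window are lost. Some true events are lost where the swab was late or at first falsely negative, which is why the window should be varied. Swab and sample dates are needed; the protocol lists laboratory data in general terms, so their presence in the data mart is inferred, not stated, and should be confirmed first.

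### Does requiring each patient's own verbal consent undermine a consecutive, partly retrospective cohort?

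*Protocol*

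**What the plan says.** Under Study design the Protocol describes a "Retrospective and prospective observational study". Under Population it enrols "All consecutive patients hospitalized" at the centre since 1 March 2021 who have a SARS-CoV-2 diagnosis and at least one troponin value. The same paragraph states that "each patient will verbally declare the consent" before at least two witnesses, and explains that signing is not possible because of "contamination of papers by SARS-CoV-2". It names three forms: consent to the use of data and samples for research, general consent to care, and the health-dossier form. Inclusion criteria lists "Verbal informed consent" without exception.

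Under Variables and procedures, the in-hospital data to be extracted include "length of hospitalization, use of glucocorticoids or antibiotics, death". Secondary endpoints, item 1, builds its composite from ventilation, intensive care, length of stay, "use of glucocorticoids or antibiotics, and death".

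On governance, Data privacy and data protection says "The guidelines for data privacy are covered by two main documents", neither of which is at hand. It adds that consent procedures conform to the European data-protection rules.

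**The concern.** A retrospective cohort and personal consent from every member sit uneasily together. Reference 14 is dated 2022, so the text was completed after at least ten months of eligible admissions. For those patients the Protocol does not say whether the consent is one already given during the stay or one still to be obtained. The future tense, taken literally, suggests the latter. In that case nobody who had already died in hospital could enter, and the cohort would be selected on a component of the first secondary endpoint.

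Even if consent was given during the stay, a patient who arrived unable to speak might never have been asked. Such patients are likely to be among those who were ventilated, admitted to intensive care or died. Leaving them out could distort the association between myocardial injury and the in-hospital composite, and the cohort would not be consecutive in the fullest sense.

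**Working it through.** **When is consent taken?** Two readings are possible.

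- *During the index stay.* The only reason given for the verbal form is contamination of paper, which applies while the patient is infectious and not to someone contacted months after discharge. By their titles, two of the three forms belong to hospital care. In-hospital death is extracted from hospital databases and counted as an outcome, so patients who died are meant to be analysed. The expected 2000 patients are derived from the existing data mart together with the inclusion criteria. This suggests, without proving it, that consent status is already known for past admissions.
- *Later, at study inclusion.* Only the future tense supports this, and that is ordinary protocol style.

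The first reading is clearly the stronger.

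**Is the word consecutive contradicted?** The Population sentence is followed by an eligibility list that narrows it. That sentence also leaves out the age limit and the need for vaccination data, and these are not contradictions either. Consent is one more criterion in the same list.

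**How large could the effect be?** The Protocol gives no in-hospital death rate and no composite rate, so there is no stated figure to reproduce. N = 2000 is the Protocol's expected size, and the 25% injured is borrowed from the event fraction of one quarter in its sample-size illustration. All other inputs are assumptions.

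- Injured 500, uninjured 1500.
- In-hospital death 35% (175) versus 8% (120), 295 deaths in all.
- Share of deaths lost for want of consent: 0 to 10% in each group (L1 injured, L0 uninjured), at most about 30 patients.
- All deaths count in the composite. Length of stay is left out of it.

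With composite risks p1, p0 and death risks d1, d0:

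OR after loss = [(p1 − L1·d1)/(1 − p1)] ÷ [(p0 − L0·d0)/(1 − p0)]

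For a common composite, 95% versus 85%, the full cohort gives (0.95/0.05)/(0.85/0.15) = 3.35. SE(log OR) = √(1/475 + 1/25 + 1/1275 + 1/225) = 0.218, so the 95% CI is 2.19 to 5.14. With 10% lost in both groups, (0.915/0.05)/(0.842/0.15) = 3.26.

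| Outcome (injured vs uninjured) | Full cohort (95% CI) | 10% lost in both | 10% of injured deaths only | 10% of uninjured deaths only |
|---|---|---|---|---|
| Composite 95% vs 85% | 3.35 (2.19–5.14) | 3.26 | 3.23 | 3.39 |
| Composite 60% vs 30% | 3.50 (2.84–4.32) | 3.39 | 3.30 | 3.60 |
| Death 35% vs 8% | 6.19 (4.77–8.05) | 6.19 | 5.57 | 6.88 |

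The composite moves by at most 4% in the first row (3.23/3.35) and 6% in the second (3.30/3.50). The death odds ratio moves by at most 11% (6.88/6.19), and equal proportional loss leaves it unchanged. The injured fraction stays between 482.5/1982.5 = 24.3% and 500/1988 = 25.2%.

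**What would it take to matter?** For death alone, SE(log OR) = 0.134. The odds ratio reaches its own 95% limit when 1 − exp(−1.96 × 0.134) = 23% of deaths are lost in one group and none in the other. The threshold is 21% if death is 45% versus 12%, and 27% if it is 25% versus 5%.

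**The case for a change.** The strongest case is that eligibility belongs in the protocol and is not left to an analysis plan, so the later-consent reading should be excluded in words. Its cost would be real. By the same formula, losing half of all deaths in both groups takes the composite odds ratio from 3.35 to 2.87, or from 3.50 to 2.86. Losing all of them, possible only if the whole cohort were retrospective, gives 2.34 and 1.99. The last figure lies outside 2.84 to 4.32, and death could then not be estimated at all. The primary analysis would not be immune: with a true predictor odds ratio of 2.0 and assumed death risks of 2%, 8%, 15% and 35% (neither predictor nor injury; predictor only; injury only; both), the observed value is 1.84 with half of the deaths lost and 1.63 with all lost.

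Those figures belong to the later-consent reading or something close to it, which the text does not favour. They cannot be carried over to consent given during the stay. What stands is narrower: the Protocol is silent on the timing of consent and on patients who could not be asked. One sentence would have made this plain. The removed consent pages or the two governance documents may already contain it.

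Reporting the excluded patients by vital status and troponin status also sounds cheap. It would mean using the records of people who did not give research consent, and the approvals may not allow that.

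**Conclusion.** The concern does not call for a change. The silence is real, but the Protocol's own reasoning places consent within the infectious stay. Patients who consented and later died are then included, and only those unable to communicate before being asked remain in doubt. The eligibility list qualifies the word consecutive in the usual way.

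Under the assumed rates, losing up to 10% of deaths shifts the composite odds ratio by at most 4% to 6% and the death odds ratio by at most 11%, all within sampling error. A loss of about 23% of deaths confined to one group would be needed to take the death odds ratio outside its interval, and nothing in the Protocol points to such an imbalance. On this reading no effect on the primary predictor analysis has been shown.

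The conclusion rests on the in-stay reading and on the assumed death, composite and loss rates. If consent was in fact sought only after discharge, it would have to be revisited. As written, this is a missing detail that analysts can settle from the consent record, and it alters no planned analysis.

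### Eligibility rests on a positive swab, not on admission for COVID-19 as the objective states, so admission mix can make cardiac history look like a predictor of injury

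*Protocol*

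**What the plan says.** The Protocol describes its population in two ways.

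- **Target.** The primary objective is "To identify clinical predictors of myocardial injury in patients hospitalized for COVID-19 infection". The primary endpoint repeats the same population: injury is "defined as at least one value of hs-cTnI >99th percentile upper reference limit (16), in patients hospitalized for COVID-19 infection". The secondary objectives refer to the index hospitalization for COVID-19.
- **Enrolled.** The Population section takes all consecutive inpatients from March 1, 2021 "with a diagnosis of SARS-CoV-2 infection (≥ 1 positive nasopharyngeal swab") who have at least one troponin value. The inclusion criterion is "Overt COVID-19 infection (molecular nasopharyngeal swab positive for SARS-CoV-2 ≥ 1"). The troponin criterion is "Patient with at least a high sensitivity Troponin I measured during hospitalization course".

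The exclusion criteria cover age, missing troponin and missing vaccination data only. The sample-size paragraph speaks of patients in hospital *with*, not *for*, COVID-19. The data listed under Variables and procedures include comorbidities, vital signs and symptoms at admission, laboratory values, blood gases and radiological reports. Reason for admission and discharge diagnosis are not listed.

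**The concern.** The word *overt* suggests clinical disease, but the parenthesis after it equates it with one positive molecular swab, so it excludes nobody whom the swab lets in. A patient admitted for an acute coronary syndrome who happens to test positive qualifies once a troponin is measured. The endpoint asks only for one value above the limit, with no requirement that the rise follow COVID-19 or be attributable to it, so such a patient is likely to count as an injury case because of the admission diagnosis.

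If patients of this kind have both more cardiac history and more injury than those admitted for COVID-19, pooling the two groups creates an association between history and injury even where neither group has one. That association would then be reported as a predictor of myocardial injury in patients hospitalized for COVID-19, a population to which it need not apply.

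**Working it through.** **Text.** Each clause that could restrict the cohort to admissions for COVID-19 was checked.

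| Place in the Protocol | Restricts by cause of admission? |
|---|---|
| Primary objective, primary endpoint | Yes, in wording |
| Population | No: swab plus troponin |
| Inclusion criteria | No: *overt* is defined by the swab |
| Exclusion criteria | No |
| Endpoint definition of injury | No: any value above the limit |

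The restriction is stated in the aim and implemented nowhere. The Protocol gives no figure for the incidental share, so there is no figure of its own to reproduce.

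**Illustration of size.** Only N (about 2000) and the two-sided 0.05 level come from the Protocol. The rest is assumed:

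- incidental share s: 2% to 30%;
- injury: 22% in admissions for COVID-19; i = 35% or 45% in incidental admissions;
- coronary disease: 15% and h = 30% or 40% respectively;
- odds ratio of coronary disease for injury within each group: 1.0.

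Pooled cell proportions:

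- A (disease, injury) = (1−s)(0.15)(0.22) + s·h·i
- B (disease, no injury) = (1−s)(0.15)(0.78) + s·h·(1−i)
- C (no disease, injury) = (1−s)(0.85)(0.22) + s·(1−h)·i
- D (no disease, no injury) = (1−s)(0.85)(0.78) + s·(1−h)(1−i)

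OR = AD/(BC); SE(ln OR) = √[(1/A + 1/B + 1/C + 1/D)/N]; z = ln OR/SE; rejection probability = Φ(z − 1.96) + Φ(−z − 1.96).

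Worked case, s = 20%, i = 45%, h = 40%:

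- A = 0.0264 + 0.0360 = 0.0624
- B = 0.0936 + 0.0440 = 0.1376
- C = 0.1496 + 0.0540 = 0.2036
- D = 0.5304 + 0.0660 = 0.5964
- OR = (0.0624 × 0.5964)/(0.1376 × 0.2036) = 1.33
- SE = 0.122, z = 0.284/0.122 = 2.32, rejection 64%

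Across the range:

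| Incidental share | Mildest inputs (i 35%, h 30%) | Strongest inputs (i 45%, h 40%) |
|---|---|---|
| 0% | OR 1.00, 5% | OR 1.00, 5% |
| 2% | OR 1.02, 5% | OR 1.05, 6% |
| 5% | OR 1.04, 6% | OR 1.12, 12% |
| 10% | OR 1.07, 8% | OR 1.21, 29% |
| 20% | OR 1.12, 13% | OR 1.33, 64% |
| 30% | OR 1.14, 18% | OR 1.39, 81% |

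**Sensitivity to the inputs.** Suppose instead that the incidental group is wholly cardiac. Take prior cardiac disease of 25% and injury of 25% in admissions for COVID-19 (the latter is the event fraction in the Protocol's own worked example), against 50% and 60% (mild) or 70% and 80% (strong) in the cardiac group. A 2% share then gives OR 1.05-1.14 (rejection 7%-20%), 5% gives 1.11-1.33 (16%-75%) and 10% gives 1.21-1.63 (42%-100%). The direction is stable; the size depends on who the incidental patients are.

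**The case against.** **The size is assumed.** Apart from N and the significance level, every input is an assumption. At a 2-5% share, under the first set of inputs, rejection is 5%-12%, close to nominal. This stands, and it is why the range must start below 10%. A reader might infer that the primary result is known to be seriously biased. The document gives no share from which that could be concluded.

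**The figures are univariable.** The Protocol also plans multivariable logistic regression, and admission symptoms, blood gases and radiology partly carry the reason for admission. Adjustment may shrink the artefact. It need not remove it, because reason for admission is not a listed variable.

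**A predictor in the enrolled cohort is not false for that cohort.** The endpoint makes no attribution to COVID-19, and early risk assessment is among the stated uses. In a swab-positive inpatient cohort, coronary disease that marks higher risk is a genuine predictor. This also stands. The defect is a mismatch between the stated and the enrolled population, and rewording the objective would cure it.

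**Other consequences are tempting to add.** A reader might infer that respiratory severity markers are pushed down, that the 12-month MACE comparison is distorted by a given amount, or that incidental cardiac patients nearly always have troponin measured. The first two are plausible but were not computed; the third is not in the document.

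**The absence of a sensitivity analysis is not itself a fault.** Such an analysis is often left to an SAP, and none is shown. The population and eligibility criteria, however, are for the Protocol to state, and there they disagree.

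**Conclusion.** The point holds as a mismatch between objective and eligibility. Followed as written, the plan studies inpatients with a positive swab and a measured troponin, and describes them as patients hospitalized for COVID-19. Cardiac history can then emerge as a predictor through admission mix alone.

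Under the first set of assumptions the pooled odds ratio is 1.02-1.12 (rejection 5%-12%) at a 2-5% incidental share and 1.07-1.39 (8%-81%) at 10-30%. These figures assume no association within either group, a univariable model and N = 2000. They show what could happen, not what the bias in this cohort is.

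A reader might also infer that the restricted cohort must become the primary analysis set. The documents do not require that. Classifying on symptoms and radiology selects on candidate predictors, and it could drop COVID-triggered cardiac presentations that belong to the study question.

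**What to change.** Align the objective, the endpoint and the inclusion criterion in one of two ways.

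- **(a) Keep the objective.** Derive an admission-reason variable (for COVID-19, or incidental positive swab) from the admission symptoms and radiological reports already extracted, plus the discharge diagnosis if it is available. Report the primary and 12-month analyses in the for-COVID-19 subgroup alongside the whole cohort.
- **(b) Keep the cohort.** Reword the objective, the endpoint and the conclusions to patients hospitalized with SARS-CoV-2 infection.

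Option (a) costs one derived variable, with some misclassification, and lower precision in the restricted analysis. The listed data support it for symptoms and radiology; the discharge diagnosis would have to be confirmed as obtainable. Option (b) costs only wording, but it gives up the claim about patients admitted because of COVID-19.
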